### 2. Primary Endpoint: Completion of MeTree

- a. Implementation endpoint: Report the number and percentage of participants who completed MeTree out of the reach population. As single-arm implementation endpoint, no inferential statistics will be used.

### 3. Secondary Endpoint 1: EHR-based identification of hereditary risk pre- and post-MeTree

- a. **Hypothesis:**

- i.  $H_0$ : MeTree has no impact on identification of patients at high risk for hereditary cancer
- ii.  $H_A$ : MeTree impacts the identification of patients at high risk for hereditary cancer

- b. **Analysis:** Descriptive statistics (counts and percentages) will be used to describe the EHR-based indication for increased cancer risk (Variable 7: presence of a personal or family history codes) for the two study time periods: pre-study consent period (T0-T1) to the post-study consent period (T1-T2) within the effectiveness population. Contrast the EHR-based determination of high risk for cancer (Variable 7), between the pre-study consent period (T0-T1) to the post-study consent period (T1-T2) using the McNemar test for paired observations, test statistic and p-value will be reported.

**4. Secondary Endpoint 2:** Genetic counseling appointment length for participants who used MeTree and for randomly selected patients from the same clinic who did not use MeTree.

a. **Hypothesis:**

- i.  $H_0$ : Using MeTree prior to genetic counseling has no impact on genetic counseling appointment length
- ii.  $H_A$ : Using MeTree prior to genetic counseling affects genetic counseling appointment lengths

b. **Analysis:** Descriptive statistics (mean, standard deviation, median and IQR or counts and percentages) will be used to summarize appointment lengths by intervention group. Differences in genetic counseling appointment length between intervention groups will be assessed using the Wilcoxon rank sum test, p-value will be reported

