## 2. Secondary outcomes derivations and definitions

- a. EHR-based indication for increased cancer risk, defined separate for the time periods

- i. EHR-based variables
  - 1. Variable 1: Personal history code in EHR [Yes/No]
  - 2. Variable 2: Family history code in EHR [Yes/No]
  - 3. Variable 3: Other code in EHR [Yes/No]
- ii. Derived outcomes from the EHR-based variables
  - 1. Variable 4: number of Variables 1-3 with value = Yes
  - 2. Variable 5: at least 1 of Variables 1-3 is Yes
  - 3. Variable 6: number of Variables 1 and 2 with value = Yes
  - 4. Variable 7: at least 1 of Variables 1 and 2 is Yes
- iii. Each of the variables above are defined for two time periods
  - 1. T0 - T1 = before consent through date of consent into the study
  - 2. T1 - T2 = after consent through the end of the study
- iv. Endpoint: Variable 7, at least one of personal history code or family history code, Variables 1 and 2 respectively, are met
- v. Sensitivity Endpoints:
  - 1. Variable 1: Personal history code in EHR
  - 2. Variable 2: Family history code in EHR

- b. Genetic counseling appointment times

- i. Length of genetic counseling appointments

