**5. Exploratory Sensitivity Analysis 1 (Reach population):**

a. **Analysis:** Use descriptive statistics (counts and percentages) to describe the EHR-based indication for increased cancer risk (Variable 7: presence of a personal or family history codes) for the two study time periods: pre-study consent period (T0-T1) to the post-study consent period (T1-T2) in the **Reach population**. Contrast the EHR-based indication for increased cancer risk (Variable 7), between the pre-study consent period (T0-T1) to the post-study consent period (T1-T2) using the McNemar test for paired observations, test statistic and p-value will be reported.

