**6. Exploratory Sensitivity Analysis 2 (Personal Hx Code):**

a. **Analysis:** EHR-based indication for increased cancer risk based on personal history (Variable 1), contrasting the pre-study consent period (T0-T1) to the post-study consent period (T1-T2), in both the **Effectiveness and Reach populations**. McNemar test for paired observations will be used to compare high risk identification in the pre-study period to the post-study period.

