**7. Exploratory Sensitivity Analysis 3 (Family Hx Code):**

a. **Analysis:** EHR-based indication for increased cancer risk based on familial history (Variable 2), contrasting the pre-study consent period (T0-T1) to the post-study consent period (T1-T2), in both the **Effectiveness and Reach populations**. McNemar test for paired observations will be used to compare high risk identification in the pre-study period to the post-study period.

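### Secondary Endpoint 1 applies McNemar's test to EHR codes from two unmatched time windows, so it does not test whether MeTree changes identification, and the sign of the error is undetermined

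*SAP*

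**What the plan says.** SAP III.2 (item a) introduces the outcome as "EHR-based indication for increased cancer risk, defined separate for the time periods". Variable 7 is Yes if a personal history code or a family history code is present. The two periods are given in item a.iii:

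- Pre: "T0 - T1 = before consent through date of consent into the study". No look-back length or calendar date is attached to T0.
- Post: "T1 - T2 = after consent through the end of the study".

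SAP IV.3 sets the null hypothesis as "MeTree has no impact on identification of patients at high risk for hereditary cancer" and contrasts Variable 7 "between the pre-study consent period (T0-T1) to the post-study consent period (T1-T2) using the McNemar test for paired observations" in the Effectiveness population. The same windows and test recur in IV.5 (Variable 7, Reach), IV.6 (Variable 1, both populations) and IV.7 (Variable 2, both populations). IV.7, for example, says "McNemar test for paired observations will be used to compare high risk identification in the pre-study period to the post-study period". That makes six tests in all.

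Protocol section 8 describes something different: a pre-MeTree chart review without any time limit, and a post assessment taken from the MeTree report itself, which does not depend on length of follow-up. Protocol section 10 gives a study duration of 4 years. SAP II.3.f limits EHR analyses to VUMC.

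**The concern.** McNemar's test asks whether two paired proportions are equal. That answers the question about MeTree only if, without MeTree, the two proportions would have been equal. For codes that accumulate over time this requires comparable observation time and the same treatment of old codes in both windows. The SAP secures neither:

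- T0 is open, so two programmers could choose different look-backs and both comply.
- The post window depends on enrolment date. It also opens at consent rather than at MeTree, and Protocol section 7 allows up to 12 months to complete MeTree before possible removal.
- A participant coded before consent and not coded again afterwards counts as evidence against MeTree. One whose old code is simply re-entered does not.

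These six tests are the SAP's only inferential tests of identification. A p-value from them could be reported as an effect of MeTree, or as a harm to identification, when it reflects window length and coding habits. None of the five repeats changes the windows, so they cannot reveal the problem.

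**Working it through.** **The plan's own figure.** Protocol section 8 needs 150 high-risk patients in the clinic: 150 / (0.10 × 0.50) = 3,000 completers. This reproduces. It is driven by Aim 2, covers both sites and does not depend on the windows. It matters here only as an upper bound on N.

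**What the test compares.** Let F be the share coded before consent, r the chance that a coded participant is coded again after consent, and g the chance that an uncoded participant gains a first code after consent.

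- Pre-only pairs: F(1 − r)
- Post-only pairs: (1 − F)g

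McNemar's null is F(1 − r) = (1 − F)g. With no MeTree effect, g is background coding, and nothing in the SAP makes the two sides equal. F depends on T0, g on time to study end, and r on coding practice.

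**Worked example (all rates assumed).** First-code rate 0.02 a year, T0 8 years back, post window uniform on 0.5–3.5 years, old codes re-entered with 10% yearly probability, N = 1,000.

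- F = 1 − e^(−0.16) = 0.148
- g = 1 − (e^(−0.01) − e^(−0.07))/0.06 = 0.039
- r = 1 − (0.9^0.5 − 0.9^3.5)/(3 × 0.1054) = 0.187
- Pre-only: 0.148 × 0.813 = 0.120. Post-only: 0.852 × 0.039 = 0.033.
- z = (33 − 120)/√153 = −7.0, a false decrease. The proportions coded are 0.148 before and 0.061 after.
- If the first-code rate truly doubles after consent, g = 1 − (e^(−0.02) − e^(−0.14))/0.12 = 0.076 and post-only is 0.065. Then z = (65 − 120)/√185 = −4.0, so a real gain appears as a decrease.
- If an old code counts as a standing entry still present after consent, r = 1 and pre-only is 0. With no effect, z = 33/√33 = 5.7, a false increase.

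**Range with no MeTree effect.** Assumptions: constant rate of 1–3% a year, N of 1,000 and 3,000, post window 0.5–3.5 years, exact McNemar at two-sided 0.05 (the 0.05 is from Protocol section 8; the SAP states no level), 4,000 replicates.

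| Case | Significant result |
|---|---|
| Same yearly rate in both periods, 1-year look-back | 37–100% increase |
| Same, 3-year | 23–99% decrease |
| Same, 5-year | about 95–100% decrease |
| Same, 8- or 10-year | 100% decrease |
| Same, equal fixed 2-year windows | 3–5% in total |
| 8-year record, old codes re-entered 10% yearly | 100% decrease |
| Same, 30% yearly | 77–100% decrease |
| Same, 50% yearly | 8–84% decrease |
| Same, 70% yearly | 19–76% increase |
| Same, 90% yearly | 88–100% increase |
| Same, old code treated as a standing entry | about 100% increase |

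With the 8-year record the sign turns at about 57–60% yearly re-entry. If the first-code rate truly doubles, a significant decrease is still reported in 73–100% of runs at 10% re-entry and 4–76% at 30%.

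**A second coding model** gives the same picture. Here 10–20% of patients have a codable history, coded at 0.1–1.0 a year. Equal 2-year windows reject 5%; unequal windows reject 27–100% at N = 1,000.

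**Equal windows alone are not enough.** With 1-year windows scoring any code, an 8-year record and 70% yearly re-entry, false increases are 13–74%, because the pool of already coded participants grows over time. A first-code rule is also needed.

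**The case against.** The strongest reply is that T0 naturally means the whole prior record, as Protocol section 8 suggests, so the definition is not really missing. That reading is reasonable, but it sets a pre window of possibly many years against a post window of at most about 4 years, which enlarges the mismatch. The protocol's independence from follow-up time belongs to the MeTree report, and the SAP's post measure is an EHR code.

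A reader might go further and infer that the test is biased against MeTree. The documents do not support that. It follows only if old codes are seldom re-entered and each window needs its own entry. Scoring the periods separately points that way, but a Yes/No code in the record could also be read as a standing entry, and then the error is entirely upward. The exclusion of patients with previous genetic testing or counselling at the VUMC Hereditary Cancer Clinic (Protocol section 3, SAP II.3.e) also lowers pre-consent coding and weakens any tendency to a false decrease.

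Other objections stand in part. This is a secondary endpoint in a single-arm implementation study. Counts for both periods will be reported, so a fall would be visible, though not its cause. Every rejection rate above rests on assumed coding rates. N = 3,000 is the two-site target, while these analyses use VUMC only, so the upper-end figures may overstate.

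**Conclusion.** The defect is established from the text: followed as written, the six McNemar tests do not test the stated null, and no passage cures this. With no effect they can be significant in either direction, and a real gain can appear as a loss. Confidence is high for the defect and low for its size and sign. Those depend on the look-back, the background coding rate, re-entry of old codes and how a standing entry is scored, none of which the documents give. The percentages show what is possible and do not predict this trial's result.

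Two wider inferences should be resisted. The primary endpoint, completion of MeTree, is reported descriptively and is untouched, as is the 3,000 figure. Nor are these direct tests of the protocol's hypothesis, whose post measure is the MeTree report. This should be fixed before analysis, but it does not undermine the study as a whole.

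**What to change.** In SAP III.2 (item a.iii), IV.3 and IV.5 to IV.7:

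1. Define T0. Use pre and post windows of one equal fixed length, the pre window ending at consent and the post window starting at the MeTree report (at consent for Reach).
2. Restrict to VUMC participants whose record is observable in both windows.
3. Count only first codes among participants uncoded at the start of each window, for Variable 7 and likewise for Variables 1 and 2.
4. Report each proportion and their difference with 95% confidence intervals, and let these lead. Keep any McNemar test as supportive.
5. State that biases remain in both directions. Depletion of the at-risk pool, differing underlying risk and any gap between consent and report lean against MeTree. The clinic exclusion thins pre-consent coded patients only and leans towards a false increase. Calendar trend and extra post-consent contact also remain. Label the result a pre/post association.
6. Claim no fixed false-positive rate for the revised analysis. As an illustration with 1-year windows and no effect, false increases are 1–3% without the exclusion, 4–9% if it removes an assumed 10% of pre-coded patients, and 10–56% if it removes 30%.

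The cost is SAP wording and a re-cut of the data by code date and report date. Dated codes are assumed, since codes must already be sorted by consent; a report date is assumed, since the report is logged in the study database. Late enrolees and participants with short records drop out. Power falls: with 1-year windows, a doubling of the first-code rate is detected in 36–100% of runs (N 1,000–3,000, 1–3% a year), so a real benefit may be missed.

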Once data entry in MeTree is complete all participants will receive a personalized patient report within the platform outlining their familial and genetic risk status the included medical conditions according to current evidence-based guidelines. Participants' providers will be notified via one of several methods (email without PHI, EPIC messaging, or an alert) that their patient has a MeTree clinical decision support report available in the medical chart (accessible via a SMART link). Outside providers will receive an email or letter. The templates for these messages is located in Appendix I. The process to upload the MeTree report and provide accessibility to providers is approved by the Medical Forms Committee and the Center for Health Information Management (CHIM) Committee.

As previously stated, in Aim 2 participants who are identified as at high genetic risk (n=300) will be contacted by the study nurse (as part of their standard of care) to schedule a genetic counseling appointment (Appendix J, High risk patient email). The number and length of genetic counseling appointments will be recorded in order to evaluate the change in clinic capacity for those with a pre-recorded FHH in the MeTree platform as compared to routine patients who have not participated in the study and completed MeTree. The frequency of genetic testing and outcomes of the testing will also be recorded in REDCap from data collection in the Hereditary Cancer Clinic at VUMC.

[figure not shown]
To analyze the time saved by completing MeTree prior to a clinic visit, the study team will perform a retrospective review of control patients, selected by the study team, to assess the amount of time in clinic with the genetic counselors. This will be done through time stamps in eStar and chart review. Control patients will not be a part of the study, nor will their information be shared with anyone. The study team will only review for time spent in clinic versus the study participants' clinic visits.

Additionally, genetic counselors who see participants from this study will be surveyed to better understand their perspective of the use of MeTree. This portion of the study will be in a separate IRB.

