We will use a case-control design for statistically analyses. Cases are defined as the study participants who have completed the MeTree tool (intervention). We will utilize data from the Hereditary Cancer Clinic registry (IRB # 141203) to fine patients identified at risk of a hereditary cancer syndrome in the usual care (control) and intervention conditions. The control condition utilizes historical data from the participants prior to their enrollment date in FOREST to determine the number and proportion of participants who would be identifiable as at risk without the implementation of MeTree. We believe this is the most effective method to analyze the MeTree platform's effect on hereditary cancer testing and outcomes. Power calculations estimate a sample size of up to 3,500 (minimum of 3,000) is needed to produce statistically significant results.

In the graph below, the blue line represents 90% power to detect the primary endpoint with a p-value of 0.05, the green line, 85% power, and the red, 80% power. The x-axis represents how many participants are identified as being at high risk by MeTree.

In prior studies of primary care populations, on average 20% were newly found to be at high risk (had not previously identified). However, in order to accommodate differences in a population that has a proactive hereditary cancer clinic, we used a lower estimate of 10% for the power analyses. Thus at 10% risk identification and 95% power we estimated that we would need at a minimum 1,000 participants for a single site and 2,000 participants total to detect differences in identification at the 2 sites (Meharry and Vanderbilt). In addition, these participants flow into aim 2. Based on power analysis to detect an increase in clinic capacity, we need to have 150 high risk patients who complete MeTree in Aim 1 to see a genetic counselor in the hereditary cancer clinic at Vanderbilt. At a 10% identification rate and a 50% follow up rate (estimate based on literature review and the clinic's attendance rate), a minimum of 3,000 participants will need to complete MeTree in Aim 1. We are therefore enrolling 3,000-3,500 participants for this study.

Data elements considered for this analysis:

Primary Endpoint: Participant designated as high risk for cancer.

Assessment pre: chart review (any indicator prior to MeTree, not time-frame dependent)

Assessment post: MeTree report (measured when the report is generated, independent of amount of follow-up time)

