### 3. Analytical Population(s)

- a. **Reach population:** defined as the participants who were invited to use MeTree (completed baseline surveys and clicked link to use MeTree)
- b. **Effectiveness population:** defined as the participants who completed MeTree and had a clinical decision support risk report generated.
- c. **Genetic counseling population:** The genetic counseling population includes participants who completed MeTree, received a genetic counseling recommendation and completed the genetic counseling appointment. A random selection of non-study participants with genetic counseling appointments at the same clinic and in the same time frame will be selected, 1:1.
- d. See the protocol paper for additional details of these populations:  
<https://www.sciencedirect.com/science/article/pii/S1551714424002970#f0010>
- e. Study participants had to meet the following inclusion and exclusion criteria to be enrolled in the FOREST study:
  - i. Inclusion
    1. Site: VUMC, MMC
    2. Demographics: Age 18 years or older
    3. Able to read and communicate in English
    4. Willing and able to use the internet to report FHH information
    5. Current user of patient portal (VUMC specific)
  - ii. Exclusion
    1. Not a patient at VUMC or MMC sites
    2. Diagnosed with a terminal illness
    3. Unable to speak/read English
    4. Unwilling or unable to use the Internet to report their FHH information
    5. Report previous genetic testing and/or counseling through the VUMC Hereditary Cancer Clinic
- f. Analyses involving EHR -related information will be restricted to VUMC participants due to the specificity of the EHR-based outcomes.

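### Secondary Endpoint 2 compares appointment length without regard to genetic counsellor; stratifying by counsellor is a cheap safeguard against a confounding the plan would neither see nor adjust for.

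*SAP*

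**What the plan says.** SAP IV.4 compares appointment length between MeTree users and other patients of the same clinic. The alternative hypothesis has no direction: "Using MeTree prior to genetic counseling affects genetic counseling appointment lengths". The analysis is: "Differences in genetic counseling appointment length between intervention groups will be assessed using the Wilcoxon rank sum test, p-value will be reported". The only other output is descriptive summaries by group. No stratum, covariate, cluster term or interval estimate is planned.

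Controls are defined in SAP II.3.c: "A random selection of non-study participants with genetic counseling appointments at the same clinic and in the same time frame will be selected, 1:1". Protocol section 5 describes a "retrospective review of control patients, selected by the study team, to assess the amount of time in clinic with the genetic counselors". Neither text uses the counsellor as a selection factor. SAP IV.1.b compares the two counselling groups on demographics only.

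Protocol section 5 shows that there is more than one counsellor ("genetic counselors who see participants from this study will be surveyed"). Neither document says how many there are, how patients are assigned to them, or how much visit length varies between them.

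On size, Protocol section 8 says "we need to have 150 high risk patients who complete MeTree in Aim 1 to see a genetic counselor", to detect an increase in clinic capacity. It gives no effect size, SD, alpha or power for that comparison. The 0.05 in that section belongs to the protocol's primary endpoint: "the blue line represents 90% power to detect the primary endpoint with a p-value of 0.05".

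**The concern.** Visit length can depend on who runs the visit. In a randomised comparison the counsellor mix would balance on average. Here it need not. Study participants are contacted and scheduled by the study nurse (Protocol section 5), referral follows the close of enrolment (Protocol section 4), and Aim 2 adds telephone and video counselling (Protocol section 2). Controls are simply other patients of the clinic. Nothing in the plan makes the counsellor mix the same in both groups, and nothing in it would reveal a difference.

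If the mix differs, a difference in counsellor style could be reported as time saved by MeTree, or could hide a real saving. This is the only inferential test of appointment length in the SAP, and the protocol's minimum of 3,000 completers is derived from the capacity comparison that it serves.

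**Working it through.** **Inputs from the documents.** 150 MeTree patients seen by a counsellor, 10% identified, 50% follow-up and 3,000 completers (Protocol section 8); 1:1 controls, so 150 per group (SAP II.3.c); unstratified rank-sum test (SAP IV.4).

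**Assumed.** Two-sided 5% level; 6 counsellors; study visits split 35/25/15/10/10/5%; controls even (1/6 each); share of variance between counsellors ρ = 5%, 10% or 20%; normal visit lengths with total SD 1.

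**1. The plan's own figure.** 150 / (0.10 × 0.50) = 3,000, which reproduces. The 150 itself cannot be re-derived. As a benchmark, 150 per group with independent visits detects (1.960 + 0.842) × √(2/150) = 0.323 SD at 80% power, or 0.323/√0.955 = 0.331 SD allowing for the efficiency of the rank-sum test.

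**2. Why a different mix inflates the error rate.** Let p and q be the counsellor shares in the two groups, r their average and n = 150. For normal data the rank-sum test behaves nearly like a comparison of means, so:

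- True variance of the difference with no MeTree effect: ρ·Σ(p−q)² + (1−ρ)·2/n
- Variance the unstratified test assumes: (2/n)·(1 − ρ·Σr²)
- Type I error: 2·[1 − Φ(1.96/√ratio)], where ratio is true over assumed

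For the assumed split, Σ(p−q)² = 0.0336 + 0.0069 + 0.0003 + 2 × 0.0044 + 0.0136 = 0.0633, and Σr² = (0.2300 + 0.1667 + 2 × 0.1667)/4 = 0.1825.

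| ρ | True variance | Assumed variance | Ratio | Type I, formula | Type I, simulated | Stratified, simulated |
|---|---|---|---|---|---|---|
| 5% | 0.00317 + 0.01267 = 0.01583 | 0.01321 | 1.198 | 7.3% | 7.0% | 4.5–4.8% |
| 10% | 0.00633 + 0.01200 = 0.01833 | 0.01309 | 1.401 | 9.8% | 9.4% | 4.5–4.8% |
| 20% | 0.01267 + 0.01067 = 0.02333 | 0.01285 | 1.816 | 14.6% | 14.8% | 4.5–4.8% |

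Further simulation runs of the same scenario gave 8.1–8.5%, 10.1–10.7% and 15.4–15.7%. A slightly higher figure is expected where the shares hold only on average, because the chance spread of the split adds to the variance.

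**3. Size of the confounding.** The SD of the spurious difference is √(0.0633ρ): 0.056, 0.080 and 0.113 SD at the three shares. Against 0.323 SD, that is 17%, 25% and 35%.

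**4. Other patterns** (simulation, 4,000 runs per cell, 4, 6 or 8 counsellors, ρ from 5% to 20%).

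| Counsellor mix | Planned test | 
|---|
| Half the counsellors see 60% of MeTree and 40% of control visits | 5.5–11.7% |
| The same, 80% and 20% | 12–44% |
| One counsellor sees 60% of MeTree visits, controls even | 12–39% |
| Same assignment probabilities in both groups | 4.6–5.6% |
| Exactly even in both groups | 3.0–5.0% |

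The van Elteren test stayed at 4.2–5.8% throughout. With ρ = 0 every pattern stayed near 5%.

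**5. Power when the mix is balanced** (true effect 0.331 SD). With an exactly even split, stratifying gained at most 1 point at ρ = 5%, about 2 points at 10% (for example 80.8% to 83.0% with 4 counsellors) and 4 to 5 points at 20% (82.9% to 87.4% with 6). With equal probabilities but a chance split, the gain at 20% was 5 to 6.5 points.

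**The case against.** The strongest reply is that the documents point to no difference in mix. Controls come at random from the same clinic and time frame, participants are scheduled as part of standard care, and nothing says that they go to particular counsellors. If both groups reach counsellors with the same probabilities, the planned test keeps its level, even with only 4 counsellors. This stands: the inflation is conditional on an imbalance that has not been shown.

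A reader might infer that having few counsellors, or clustering as such, invalidates the test. The results do not support that. The cause is a different mix by group combined with real differences between counsellors; in the pattern with one dominant counsellor, inflation grows as the number of counsellors rises. A reader might also infer that a stated error rate is breached, but no alpha is given for this endpoint. Nor is the test seriously short of power when the mix is even: the loss is negligible to modest.

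It is also fair that this is a secondary endpoint. The SAP's primary endpoint (IV.2) is descriptive and unaffected.

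What the reply does not meet is that sharing a clinic and a time frame does not guarantee a shared counsellor mix when one group is recruited and booked through a study. As written, the plan has no means of finding out.

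**Conclusion.** The point holds as a cheap improvement to a secondary analysis, not as a demonstrated failure. The comparison is non-randomised, is blind to the counsellor in both control selection and testing, and includes no check of the counsellor mix. Under the assumed 6 counsellors, uneven split and 5% to 20% variance share, the planned test rejects a true null about 7% to 15% of the time at a nominal 5%. Milder or stronger imbalance moves this from about 5.5% to 44%. With equal assignment probabilities there is no inflation, and the benefit of stratifying is about 1 to 5 points of power, slightly more in a few cells. The number of counsellors, the split, the variance share and the 5% level are all assumptions; the sponsor can replace the first three with clinic data.

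**What to change.** - During the eStar time-stamp extraction and chart review, record the counsellor for each visit.
- Add the distribution of counsellors by group to the description of the counselling population in SAP IV.1.b.
- In SAP IV.4, replace the rank-sum test with a van Elteren test stratified by counsellor. Add a counsellor-adjusted difference in appointment length with a 95% CI, for example from a linear model with counsellor as a fixed effect. State the two-sided alpha.
- Optionally, amend SAP II.3.c so that controls are drawn within counsellor where enough non-study visits exist in the time frame. This changes the selection rule as well as the test and is not essential once the analysis is stratified.

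The cost is SAP wording and one extra extracted variable. Counsellor identity has to be available in the chart data, which the documents do not confirm. A counsellor with visits in only one group contributes nothing to the stratified comparison, so the number of visits lost this way should be reported. If the mix proves even, almost nothing is given up.
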